- Participants who receive only one dose prior to transplant and second dose at the 12 Month Post-Transplant
  Visit will be offered an Additional Study Visit at 3 months (+4 weeks) after 12 Month Post-Transplant
  Visit
- Participants who receive one vaccine dose, but their transplant surgery is postponed/rescheduled/cancelled and eventually not scheduled within 12 months of the study enrollment date, will be offered two Additional Study Visits to complete the three dose vaccine series. Additional Study Visit 1 will occur 12 months (±2 weeks) after Pre-Transplant Vaccine Visit 1, and Additional Study Visit 2 will occur 3 months (±4 weeks) after Additional Study Visit 1.

<sup>2 Pre-Transplant Vaccine Visits 1 and 2 are optional, guided by the timing of surgery and feasibility of additional study-related visits. Participants who do not have Pre-Transplant Vaccine Visits 1 and/or 2 will still receive the complete 3-dose series of the vaccine (the remaining vaccination(s) will occur post-transplant; see Appendix B for a detailed schedule). If the Pre-Transplant Vaccine Visits 1 and 2 occur, the following intervals must be used:

<sup>3 The 6 Month Post-Transplant Visit will occur 6 months (±2 weeks) after the participant's renal transplant procedure.

<sup>4 The 12 Month Post-Transplant Visit will occur 12 months (±2 weeks) after the participant's renal transplant procedure.

<sup>5 The 13 Month Post-Transplant Visit will occur 1 month (+2 weeks) after the 12 Month Post-Transplant Visit. This visit will occur only for participants who received a vaccine at the 12 Month Post-Vaccine Visit.

<sup>6 Additional Study Visit(s) will be offered for participants only for the purpose of completing their vaccine series (second and/or third doses) in the following scenarios:

- Participants who receive two vaccine doses, but their transplant surgery does not occur within 12 months of the study enrollment date, will complete an Additional Study Visit to complete the three dose vaccine series at 12 months (±2 weeks) after Pre-Transplant Vaccine Visit 1.

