#### 7.5 Post-intervention Follow-up Period

## 13 Month Post-Transplant Visit

If the participant received a vaccine dose at the 12 Month Post-Transplant Visit, the participant will return for a 13 Month Post-Transplant Visit. This visit will occur 1 month (+2 weeks) after the 12 Month Post-Transplant Visit. The following procedures will be performed during this visit:

1) Blood draw – A 10 mL blood specimen will be collected from each participant to measure HPV vaccine-type-specific antibody titers.

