### Exploratory Endpoints:

- 1) Descriptive statistics, such as probabilities and exact 95% confidence intervals, will be used to summarize probability of seroconversion at 12 months post-transplant for the following groups:
  - a) time elapsed between last vaccine dose and the transplant procedure, e.g. <3 months vs. >3 months. Different groupings will be considered based on observed (e.g. median) and clinical considerations. Time will be summarized using descriptive statistics, e.g. median, interquartile range, or range; groups defined by dosing and types of post-transplant immunosuppressant medications, as well as;
  - b) type of transplant surgery (living donor/deceased donor);
  - c) differences in Human Leukocyte Antigen (HLA) histocompatibility between donor and recipient:
  - d) differences by biological sex (i.e., male vs. female) of the transplant recipient.
- 2) Stability of HPV vaccine-type-specific geometric mean titers (GMT) at 6 and 12- months post-transplantation, and rise in HPV vaccine-type-specific GMT at the 13 month post-transplant visit.
  - a) Stability will be evaluated in relation to changes in the type-specific GMTs between the two post-transplant time points (6- and 12-months post-transplant) and reported as follows: (i) decrease: more than 2-fold decrease, (ii) stable: within 2-fold change, and (iii) increase: greater than 2-fold increase.
  - b) The magnitude of increase in type-specific GMTs at the 13-month post-transplant visit (i.e., 1 month after the booster dose) will be described in relation to the type-specific GMTs at the other post-transplant visits (6 and 12-months post -transplant). Patterns over time will also be explored using graphical techniques.
  - c) Stability, and post-booster dose increase in type-specific GMTs will also be described in relation to the number of vaccine doses (1, 2 or 3) received in the pre-transplant period.
- 3) Vaccine safety profile and allograft rejection/opportunistic infections will be summarized using descriptive statistics, stratified by number of vaccine doses and time between the last vaccine dose and the transplant procedure.
- 4) HPV detection in samples from the anogenital, and oral cavity specimens at baseline (prevaccination) and at 6- and 12-months post-vaccination, overall and by number of vaccine

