12 Months Post- Transplant Visit	Vaccine #2 12 months (±2 weeks) after Transplant Surgery	Vaccine #3 • 12 months (±2 weeks) after Transplant Surgery	12 months (±2 weeks) after Transplant Surgery	1~				
13 Months Post- Transplant Visit	• 1 month (+2 weeks) after 12 Months Post- Transplant Visit	• 1 month (+2 weeks) after 12 Months Post- Transplant Visit	~~	~~				
Additional Study Visit 1	Vaccine #3 • 3 months (+4 weeks) after 12 Months Post- Transplant Visit		~	Vaccine #2  ■ 12 months (±2 weeks) after Pre- Transplant Vaccine Visit 1  Vaccine #3  ■ 12 months (±2 weeks) after Pre- Transplant Vaccine Visit 1  N/A, participant is notified 12 months (±2 weeks) after Pre- Transplant Vaccine Visit 1  Visit 1  N/A, participant is notified 12 months (±2 weeks) after Pre- Transplant Vaccine Visit 1  Visit 1				
Additional Study Visit 2		~~		Vaccine #3 3 months (+4 weeks) after Additional Study Visit 1				

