#### **Applicable visits:**

- 6-months post-transplant visit
- 12-months post-transplant visit
- 13-months post-transplant visit (to be conducted only if, and 1-month after, any original scheduled or rescheduled in-person 12-month post-transplant visit is conducted).

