- 4. **13-months post-transplant study visits**: This visit will also be considered an optional one and can now be rescheduled to occur one month (+/- 2 weeks) after the rescheduled 12-month post-transplant visit, only for participants who have received the booster injection.
- 5. **Visit procedures:** All procedures in Section 7 "CLINICAL EVALUATIONS AND PROCEDURES" corresponding to the rescheduled visits will be conducted as outlined. In addition, cervical/vaginal, and blood specimens may occur for eligible and consenting participants for the 6-months, 12-months, and 13-months (finger stick only) post-transplant visits.
- 6. **Specimen Management:** The finger-prick collection method will yield dried blood spot collection that will be stored in the biorepository at Cedars Sinai Medical Center for future analysis for the HPV serological analysis for the primary and secondary endpoints. The cervical/vaginal specimens will be used per protocol for analysis of secondary aims.
- 7. **Participant reimbursement**: For participants seen under the COVID-19 Contingency Plan compensation will be per protocol.

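### Appendix G lets the post-booster blood draw fall up to two weeks early, but Section 13.5 still calls the result a one-month rise and has no rule for actual days since the booster

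*Combined protocol and SAP*

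**What the plan says.** **Regular schedule.** Section 7.5 says of the 13-month visit: "This visit will occur 1 month (+2 weeks) after the 12 Month Post-Transplant Visit". Section 7.1, footnote 5, gives the same window, and Appendix B repeats it for coordinators as "1 month (+2 weeks) after 12 Months Post- Transplant Visit". None of the three allows an early draw. Footnote 5 also restricts who attends: "This visit will occur only for participants who received a vaccine at the 12 Month Post-Vaccine Visit". Section 7.5 carries the same restriction.

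**COVID-19 contingency.** Appendix G item 4 makes the visit optional and lets it be "rescheduled to occur one month (+/- 2 weeks) after the rescheduled 12-month post-transplant visit", "only for participants who have received the booster injection". The list of applicable visits in the same appendix says the 13-month visit is "to be conducted only if, and 1-month after, any original scheduled or rescheduled in-person 12-month post-transplant visit is conducted"; it gives no tolerance and does not mention the booster.

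**Analysis.** Section 13.5, exploratory item 2(b), describes "The magnitude of increase in type-specific GMTs at the 13-month post-transplant visit (i.e., 1 month after the booster dose") against the 6- and 12-month titres, and adds that patterns over time will be explored graphically. It does not mention actual days since the booster or samples outside the regular window. Section 7.7 gives the purpose of the draw: to capture the anamnestic response to the booster.

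**The concern.** The booster is given at the 12-month visit, so the window around the 13-month visit fixes the time since the booster. That time is part of the definition of the quantity being estimated. Under Appendix G, a draw at about two weeks and a draw at about six weeks are both valid 13-month samples, and Section 13.5 gives both the same one-month label.

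For participants boosted after transplant this is the only scheduled post-booster titre, because the Additional Study Visits in Section 7.6 involve vaccination only. The group is also small. Sections 13.3 and 13.4 expect 24 to 28 evaluable participants, and those with three pre-transplant doses have no 13-month visit. A few early draws could move a GMT in a group of that size. At stake is whether the reported rise describes immune memory at one month, or a mixture of times that differs from the label and from what another study would report.

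**Working it through.** **Inputs**
- Regular window: 1 month, +2 weeks (Sections 7.1 footnote 5 and 7.5; Appendix B).
- Contingency window: 1 month, +/- 2 weeks (Appendix G item 4).
- Day 0 is the 12-month visit, at which the booster is given (Section 7.4).
- Length of a month, M: not defined in the documents. Assumed 28 to 31 days, with 30 as the working value.

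**Formulas**
- Regular window: day M to day M + 14.
- Appendix G window: day M - 14 to day M + 14.

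| M (days) | Regular | Appendix G | Earliest draw as share of the month, (M - 14)/M |
|---|---|---|---|
| 28 | 28 to 42 | 14 to 42 | 14/28 = 50% |
| 30 | 30 to 44 | 16 to 44 | 16/30 = 53% |
| 31 | 31 to 45 | 17 to 45 | 17/31 = 55% |

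The width doubles from 14 to 28 days. The share of the Appendix G window that lies before the earliest regular day is 14/28 = 50%, whatever M is. In weeks, the range runs from 14/7 = 2.0 to 45/7 = 6.4, or about 2 to 6 weeks.

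Appendix G also widens the 12-month visit itself to as much as +/- 6 months. That does not enter here, because item 4 counts from the rescheduled 12-month visit.

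**Direction of any bias.** Let R be the true one-month fold rise, f the share of samples drawn early, and s the share of the one-month log rise that an early sample shows. The reported geometric mean rise is then R^(1 - f + f*s).
- s below 1 (titres still rising at the early draw): the reported rise is too low.
- s = 1 (titres already at their one-month level): no change.
- s above 1 (peak reached earlier and titres falling by one month): the reported rise is too high.

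The documents give neither f nor s, so the formula yields a direction under each condition and no size.

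**The case against.** **The other side.** Appendix G presents itself as a list of permitted modifications, so the wider window is declared and is not an accidental contradiction. A tolerance of +/- 2 weeks is the protocol's norm for the 6- and 12-month visits, and the wish to combine study visits with clinical care can pull a date either way. The endpoint is exploratory and descriptive, with no test or decision attached. Excluding early samples costs data from a small group, and reporting actual days might be enough.

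**What stands.** The change is declared and the impact is small. But the declaration authorises the draw and leaves the label in Section 13.5 untouched. The same 14 days also weigh differently here. With 30-day months they are 14/180 = 8% of the 6-month interval and 14/360 = 4% of the 12-month interval, but 14/30 = 47% of the one-month interval. The reasons Appendix G gives, closed clinics and deferred visits, explain lateness; it gives none for drawing this sample early.

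**Stronger readings that the documents do not support**
- *That Appendix G allows the sample without a booster.* A reader might infer this from the list of applicable visits. Its wording sets a necessary condition and grants no permission; item 4 limits the visit to booster recipients, and item 5 keeps the Section 7 procedures. Section 8.3 does offer off-agent participants a 13-month visit when a dose may not be possible, but item 2(b) is by its own terms a post-booster quantity.
- *That the response is sampled before it is complete, with a known loss.* Suppose log titre rises linearly. With a lag of 3 days and a peak at day 21, a day-16 sample shows (16 - 3)/(21 - 3) = 0.72 of the log rise. With a lag of 7 days and a peak at day 30, it shows (16 - 7)/(30 - 7) = 0.39. A true 10-fold rise would then read 10^0.72 = 5.3-fold or 10^0.39 = 2.5-fold. In the same model with a peak at or before day 16, nothing is lost. The documents give no lag or peak, so these figures are not a finding.
- *That Section 13.5 pools every sample collected.* It is silent, and silence is not a pooling rule.

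**Conclusion.** The point holds as a mismatch between a permitted sampling window and the label of the estimate. Appendix G moves the earliest valid draw from about day 30 to about day 16, doubles the window, and places half of it before anything the regular schedule allows. Section 13.5 keeps the one-month label and has no rule for actual time. This rests only on the text and on taking a month as 28 to 31 days.

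A downward bias in the reported rise is conditional on titres still climbing at about two weeks, which the documents neither state nor exclude. The effect is confined to exploratory endpoint 2, among participants boosted at 12 months. The primary and secondary endpoints are untouched. The plan should be changed because the correction is cheap, not because a main conclusion is at risk.

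**What to change.** 1. **Reconcile the windows.** Bring Appendix G item 4 into line with Sections 7.1 and 7.5 and Appendix B on this blood draw by keeping the forward-only lower limit. If the contingency needs more flexibility, put it on the late side. The list of applicable visits can repeat the booster condition from item 4, so that the two places in the appendix read alike. No dose timing is involved.
2. **Add an analysis rule to Section 13.5 item 2(b).** Compute the one-month rise from participants who received the booster and were sampled within the Section 7.5 window, counted in actual days since the booster. Report earlier samples separately, each with its days since the booster.

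If the two-sided window is kept for operational reasons, the second change alone would still make the label accurate.

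Cost: about one line in Appendix G and two sentences in Section 13.5. The downside is that a few early samples leave the headline rise in an already small subset. They remain in the report, and no collected data are lost.
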